- l. Every 3 months for the first year starting with Cycle 3 Day 1 and after 1 year the frequency will decrease to once every 6 months.
- m. Refer to [Table 17](#) (Dose-Determination Phase Segment 1), [Table 18](#) (Dose-Determination Phase Segment 2), and [Table 19](#) (Expansion Phase) for detailed pharmacodynamic sample schedules.
- n. Refer to [Table 20](#) (Dose-Determination Phase Segment 1), [Table 21](#) (Dose-Determination Phase Segment 2), and [Table 22](#) (Expansion Phase) for detailed pharmacokinetic sample schedules.

- ^o. Isolated new lesions on bone scan at <12 weeks from Cycle 1 Day 1 will be confirmed with a repeat bone scan at 6 weeks to rule out bone scan flare: refer to Prostate Cancer Clinical Trials Working Group 3 for 2+2 rule.
- ^p. Tumor assessments (CT/MRI, bone scan): The baseline tumor assessment should be performed within 28 days prior to the first dose of enzalutamide (for Dose-Determination Phase Segment 1) and/or CORT125281 (for Dose-Determination Phase Segment 2 and the Expansion Phase). The first on-study tumor assessment should be performed 8 weeks from the first dose of study treatment (CORT125281 or on-study enzalutamide, whichever is earlier) and then every 8 weeks for the first 24 weeks and every 12 weeks thereafter, at the EOT Visit (if not performed within 4 weeks), and as clinically indicated. For on-study scans, a window of ± 14 days is acceptable with the timing of the scans based on Cycle 1 Day 1.
- ^q. Includes FACT-P and questions relating to patient-reported pain. To be performed prior to dose during the following visits: Prior to initiation of CORT125281 and/or enzalutamide, at the completion of the Lead-In Period (applicable to patients in Dose-Determination Phase Segment 1 and patients in the Expansion Phase for whom food-effect will be assessed), Cycle 3 Day 1, every 3 cycles after Cycle 3 Day 1, and at the End-of-Treatment +30 Days Visit. For patients who discontinue treatment prior to disease progression, the questionnaires will be performed per the Schedule of Assessments until unequivocal progressive disease is documented.

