APPENDIX B: RESPONSE CRITERIA

Lesions should be graded using the following criteria from the Prostate Cancer Clinical Trials Working Group 3 (PCWG3) ([Scher et al. 2016](#)):

- Soft tissue lesions (lymph node, prostate, visceral)
 - Soft tissue lesions should be assessed for response rate and progression using Response Evaluation Criteria in Solid Tumors (RECIST) v1.1
- Lymph node target lesions should be recorded by as locoregional or extrapelvic (retroperitoneal, mediastinal, thoracic or other). Existing pathological lymphadenopathy will be defined per RECIST v1.1. Lymph nodes that were previously normal in size must have grown at least 5 mm in the short axis from baseline or nadir and be ≥ 1 cm in the short axis to have progressed.
- Visceral lesions should be designated separately as lung, liver, adrenal, or central nervous system.
- Bone
 - The presence or absence of bone metastases on bone scan will be documented at baseline and lesion number will be documented and assessed serially at each tumor assessment using the bone scan assessment tool.
 - For patients who develop equivocal bone lesions while on study, the use of other scanning modalities, including MRI, positron emission tomography, or other investigational scans that were not used to determine eligibility are discouraged.
 - Progression is defined as at least 2 new lesions; if equivocal, confirm by repeat bone scan 8 weeks later; response is not defined.

The type of progression (growth of existing lesions versus development of new lesions) will be documented separately by site.

The following definitions from RECIST v1.1 ([Eisenhauer et al. 2009](#)) should be used:

- Evaluation of Target Lesions
 - Complete Response (CR): Disappearance of all target lesions. Any pathological lymph nodes (whether target or non-target) must have reduction in short axis to < 10 mm.
 - Partial Response (PR): At least a 30% decrease in the sum of the diameters (SOD) of target lesions, taking as reference the baseline SOD.

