Symptomatic Skeletal Event (SSE): SSE is defined as symptomatic fracture, radiation or surgery to bone, or spinal cord compression. SSEs include only symptomatic events of clear clinical significance. Kaplan-Meier estimates of median time from date of first dose of exicorilant to the first occurrence of SSE and associated 95% CIs, will be computed by treatment regimen dose group and overall for the Safety population. Patients who are event-free will be censored at the date of their end of study/treatment + 30 days visit. Kaplan-Meier graph of the probability of the event will also be constructed by treatment group.

Radiographic progression-free survival (rPFS): For the Response-Evaluable population, rPFS will be determined from the first dose of study treatment (exicorilant and/or enzalutamide) to the date when the first site of disease is found to progress on CT, MRI, or radionucleotide bone scan per PCWG3, or death, whichever occurs first. Progression will be assessed by the Investigator using RECIST v1.1.

$$\text{rPFS (months)} = (\text{earliest date of progression, death, or censoring} - \text{date of first study treatment} + 1) / 30.4375$$

Patients who do not experience disease progression or death (due to any cause) will be right-censored at the time of the last tumor assessment date. Censoring date will be based on the date patient was last known to be alive and progression-free (i.e., last assessment date) or data analysis cutoff date, whichever occurs first. Censoring rules are summarized in [Table 3](#) below.

Table 3: Censoring Rules for the Primary Analysis of PFS

Censoring Categories	Date of Censoring
Patients who did not have baseline or postbaseline tumor assessments and did not die on or before the data cutoff date	Date of first study treatment

Patients who did not have disease progression as determined by the Investigator and did not die on or before the data cutoff date	Date of the last adequate tumor assessment on or before the data cutoff date
Patients who did not have disease progression as determined by the Investigator on or before initiation of subsequent anticancer therapy for prostate cancer and did not die on or before the data cutoff date	Date of the last adequate tumor assessment on or before initiation of subsequent anticancer therapy and on or before the data cutoff date

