Bone disease progression: For the Response-Evaluable population, bone disease progression, defined as time from first dose of study treatment (exicorilant and/or enzalutamide) to first confirmed appearance of at least 2 new bone metastatic lesions, will be estimated via the Kaplan-Meier method. Cases of equivocal progression will be confirmed by a repeat scan 8 weeks later. Patients who are alive and progression-free will be censored at their end of study visit. Median time to progression and associated 95% CIs will be summarized, overall and by treatment group. Kaplan-Meier graph of the probability of the event will also be plotted by treatment group.

Overall survival (OS): Overall survival will be calculated as the time from the first dose of study treatment (exicorilant and/or enzalutamide) to the date of death from any cause. Deaths that occur on or before the data cutoff date will be considered an event. If a patient has not died before the analysis cutoff date, OS will be censored at the date of last contact on or before the data cutoff date. The last contact date will be derived as follows:

Source Data Conditions	Source Data Conditions
Date of randomization	No condition
Last contact date/last date patient known to be alive from Long-Term Follow-Up eCRF	Use if patient status is reported to be alive Do not use if patient status is reported unknown
End of study	Not lost to follow up
Start/end dates of postbaseline antineoplastic therapy	Nonmissing medication/procedure term
Start/end dates from drug administration record	Nonmissing dose. Doses of 0 are allowed.
End of treatment date from the End of Treatment eCRF	No condition
Investigator overall tumor response assessment date	Evaluation is marked as done.
Laboratory/PK collection dates	Sample collection marked as done.
Vital signs date	At least 1 nonmissing parameter value
ECOG performance status date	Nonmissing ECOG performance status
Start/end dates of adverse events	Nonmissing verbatim term
Physical examination	Evaluation is marked as done.
ECG	Evaluation is marked as done.

The OS in months is defined as follows:

$$\text{OS (months)} = (\text{earliest date of death or censoring} - \text{date of first study treatment} + 1) / 30.4375$$

Median, 25th and 75th percentiles of OS, in months, with 95% CIs will be summarized and plotted graphically by treatment arm and overall using the Kaplan-Meier method.

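### Table 16 footnote o and Appendix B disagree on when, and how soon, new bone-scan lesions must be confirmed, and the SAP neither settles this nor says which scan dates the event

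*Protocol*

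**What the plan says.** - **Protocol Appendix B, Bone.** "Progression is defined as at least 2 new lesions; if equivocal, confirm by repeat bone scan 8 weeks later; response is not defined". Section 6.7 points to this appendix for response assessment.
- **Protocol Table 16, footnote o**, attached to the radiographic assessment row. "Isolated new lesions on bone scan at <12 weeks from Cycle 1 Day 1 will be confirmed with a repeat bone scan at 6 weeks"; the stated purpose is "to rule out bone scan flare: refer to Prostate Cancer Clinical Trials Working Group 3 for 2+2 rule". The documents define neither *isolated* nor the content of the 2+2 rule.
- **SAP 9.1, bone disease progression.** The event is the "first confirmed appearance of at least 2 new bone metastatic lesions". The next sentence reads: "Cases of equivocal progression will be confirmed by a repeat scan 8 weeks later".
- **SAP 9.1, rPFS.** Time runs "to the date when the first site of disease is found to progress on CT, MRI, or radionucleotide bone scan per PCWG3", or to death if earlier. Neither this text nor the censoring rules in SAP Table 3 give a lesion count or a confirmation step for bone.
- **Scan timing (Table 16, footnote p).** The first on-study assessment is 8 weeks from the first dose of study treatment, with a window of ±14 days timed from Cycle 1 Day 1.

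**The concern.** Footnote o treats new lesions on an early bone scan as possible flare, to be checked before they are believed. The bone rule in Appendix B has no such step: what matters there is whether the lesions are equivocal, not when they appear. A site grading from Appendix B and a site following the schedule footnote could therefore classify the same week-8 scan differently.

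rPFS, the proportion progression-free at 4 months and time to bone disease progression are all secondary measures that depend on this classification. If flare is scored as progression, a patient who is benefiting contributes an early event. Section 3.1 has tumor assessments documented only until progression, so later scans may not be there to correct the call. Section 4.4.1 also lists progressive disease as a reason to stop study treatment, so the discontinuation wording touches the same question.

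**Working it through.** The plan gives no figure to reproduce. The check is a comparison of the texts followed by date arithmetic.

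**1. The rules side by side**

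| | Footnote o | Appendix B | SAP 9.1 bone progression | SAP 9.1 rPFS |
|---|---|---|---|---|
| What triggers a repeat | Isolated new lesions before week 12 | Equivocal finding | Equivocal finding, though the event itself must be confirmed | Not stated; refers to PCWG3 |
| Repeat interval | 6 weeks | 8 weeks | 8 weeks | Not stated |
| Early-scan step | Yes | No | No | No |
| Date of the event | Not stated | Not stated | Not stated | Date progression is found |

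I read the 6 weeks in footnote o as counted from the scan that showed the lesions. An equivocal, isolated new lesion before week 12 meets both protocol triggers and is given two different repeat dates. Two unequivocal new lesions at week 8 are progression under Appendix B. They await confirmation under footnote o, provided that *isolated* covers them.

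**2. Is the first scan always in the early period?**

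- No lead-in: 8 ± 2 = weeks 6 to 10 after Cycle 1 Day 1, always below 12. The second scan, 16 ± 2 = weeks 14 to 18, never is.
- Food-effect patients, if counted from Day -7: 7 ± 2 = weeks 5 to 9, always below 12.
- Segment 1 patients with the 28-day lead-in, if counted from the first enzalutamide dose: 4 ± 2 = weeks 2 to 6. Their second scan, 12 ± 2 = weeks 10 to 14, may also fall below 12.

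So the first scan lies in the period for every Segment 2 and Expansion patient, about 20 + 40 = 60.

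**3. Effect on the 4-month proportion**

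- Landmark: 4 × 30.4375 / 7 = 17.4 weeks.
- A week-8 event under the SAP's rPFS formula, no lead-in: (56 + 1) / 30.4375 = 1.9 months.
- One patient in a cohort of 20: 1/20 = 5 percentage points. This is a maximum per patient, because that patient might have progressed by 4 months anyway.

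**4. Effect of the interval and of the dating rule**

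| First scan | Repeat at +6 weeks | Repeat at +8 weeks |
|---|---|---|
| Week 6 | Week 12 | Week 14 |
| Week 8 | Week 14 | Week 16 |
| Week 10 | Week 16 | Week 18 |

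For a first scan at week 10, the two repeats fall either side of 17.4 weeks. If the event were dated at the confirming scan, the same confirmed progression would count as an event at 4 months under one interval and as event-free under the other. Dated at the first scan, it is an event by 4 months under either interval.

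**The case against.** The best defence is that the passages can be read together: footnote o as a specific early-scan rule, Appendix B as the general one. Section 6 makes adherence to the schedule of assessments mandatory, both passages invoke PCWG3, and PCWG3 is named throughout as the response standard. Appendix B also mentions flare. This is a possible reading, but neither Appendix B nor the SAP states it, and it leaves the 6- and 8-week intervals unreconciled. The flare wording in Appendix B sits under RECIST target lesions and concerns healing of pre-existing lesions, not the bone rule.

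*Isolated* is a fair objection. It could mean a single lesion, or bone lesions without progression elsewhere. On the first meaning, two clear new lesions at week 8 would fall outside footnote o. That weakens the claim of a head-on contradiction and is itself a reason to define the word.

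A reader might also infer three stronger things that the documents do not support:

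- **That the SAP lets unconfirmed early lesions count.** It does not say so: bone disease progression requires a confirmed appearance, and rPFS defers to PCWG3. The SAP's defect is that it does not specify confirmation for early scans.
- **That a progression call necessarily ends treatment.** Section 4.4.1 lets a patient with overall clinical benefit remain if the Medical Monitor and the Investigator agree.
- **That the loss is 5 to 15 points per cohort.** That would follow from an assumed flare rate of 5 to 15% (1 to 3 of 20 patients), but only if every flare showed at least two lesions, none was called equivocal, and every site passed over footnote o. The documents give no flare rate.

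**Conclusion.** The concern holds as a conflict between footnote o and Appendix B over trigger and interval, and as a gap in the SAP. Following Appendix B literally can score possible flare on the first scan as an rPFS event that footnote o, unless *isolated* is read narrowly, would hold for confirmation. The SAP requires confirmation for one endpoint, describes it only for equivocal cases, says nothing specific for rPFS, and leaves the dating of the event open.

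The size is up to 5 points on the 4-month progression-free proportion for each affected patient in a 20-patient cohort; the number of such patients cannot be derived from the documents. The endpoints concerned are secondary and summarised descriptively, and the Expansion sample size rests on PSA response, so the main design is not affected. The point should be fixed because different sites could otherwise apply different endpoint definitions.

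**What to change.** Write one bone-progression endpoint rule and use it in footnote o, Appendix B and SAP 9.1, for both rPFS and bone disease progression:

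1. Define *isolated*.
2. Carry the early-scan confirmation step into Appendix B and the SAP, so that the new lesions it covers count as an endpoint event only if confirmed.
3. State one repeat interval in all three places. The sponsor should choose it.
4. Date a confirmed event at the first scan that showed the lesions. If it is not confirmed, treat that scan as non-progression.
5. Check that the discontinuation wording in Section 4.4.1 is consistent with the reconciled rule.

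The cost is mainly wording. Some early progression calls will wait for the confirming scan, and if *isolated* is defined broadly a few repeat scans may be added.

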APPENDIX C: EXAMPLES OF MEDICATIONS AND FOODS THAT ARE PROHIBITED OR TO BE USED WITH CAUTION

The following medications and foods are examples of prohibited medications/foods or medications/foods to be used with caution during the study:

	Prohibited	Use with Caution
CYP3A4 Inducers	St. John's wort Carbamazepine, phenytoin, rifampin	Bosentan, efavirenz, etravirine, modafinil, nafcillin
CYP3A4 Inhibitors	Grapefruit and Seville oranges (including marmalade and juices made from these fruits) Boceprevir, clarithromycin, conivaptan, indinavir, itraconazole, ketoconazole, lopinavir/ritonavir, mibefradil, nefazodone, nelfinavir, posaconazole, ritonavir, saquinavir, telaprevir, telithromycin, voriconazole	Amprenavir, aprepitant, atazanavir, ciprofloxacin, darunavir/ritonavir, diltiazem, erythromycin, fluconazole, fosamprenavir, verapamil
CYP3A4 Substrates	Alfentanil, aprepitant, astemizole, budesonide, buspirone, cisapride, conivaptan, cyclosporin, darifenacin, darunavir, dasatinib, dihydroergotamine, dronedarone, eletriptan, eplerenone, ergotamine, everolimus, felodipine, fentanyl, indinavir, fluticasone, lopinavir, lovastatin, lurasidone, maraviroc, midazolam, nisoldipine, pimozide, quetiapine, quinidine, saquinavir, sildenafil, simvastatin, sirolimus, tacrolimus, terfenadine, tolcapant, tipranavir, triazolam, ticagrelor, vardenafil	
CYP2C8 Inducers	Rifampin	
CYP2C8 Inhibitors	Gemfibrozil	Glimepiride, tolbutamide ^a
CYP2C9 Substrates	Celecoxib, phenytoin	Warfarin ^b
CYP2C19 Substrates	S-mephenytoin, omeprazole, lansoprazole, esomeprazole ^c , clobazam	
Corticosteroids or GR modulators	Mifepristone or other GR antagonists	Topical or oral corticosteroids
QT-prolonging medications		Substitute or eliminate QT-prolonging medications, when possible (https://www.crediblemeds.org/)

BID, twice daily; CYP, cytochrome P450; GR, glucocorticoid receptor.

^a. For patients receiving sulfonylureas, conduct close glucose monitoring to assess for diabetic control.

^b. If co-administration of the study regimen with warfarin cannot be avoided, conduct additional international normalized ratio monitoring.

^c. Ranitidine 75 mg BID may be used as an alternative to a proton pump inhibitor, with the dose of ranitidine taken 1 hour after CORT125281 administration.

The above is not an exhaustive list. For a more comprehensive list or to review specific medications, see the following links:

<http://www.fda.gov/Drugs/DevelopmentApprovalProcess/DevelopmentResources/DrugInteractionsLabeling/ucm080499.htm> and <http://medicine.iupui.edu/clinpharm/ddis/main-table/>

APPENDIX D: STANDARD DIET

The suggested meal content should consist of approximately 520 Kcal with approximately 30% calories from fat (total grams of fat, approximately 17 grams). The approximate content of the breakfast meal and time and duration of consumption will be recorded in the study records.

A sample meal description is as follows:

Standard American Heart Association Healthy (Low-Fat) Breakfast

1 box cereal (30-40 g)

Skim milk (240 mL)

1 boiled egg

1 slice toast (15 g)

Margarine (10 g)

Total calories, approximately 520 Kcal

APPENDIX E: SUMMARY OF CHANGES

Significant changes in Amendment 5 of the protocol compared with Amendment 4 of the protocol are summarized below with additional details in [Table 23](#). Minor editorial or stylistic changes made for consistency are not summarized and are not shown in the redline version of the amendment.

- Added a double-blind portion (Segment 2) to the Dose-Determination Phase to determine the recommended dose (RD) for CORT125281 administered once daily (QD) under fed conditions.
- Revised the wording for the other portions of the study for clarity, upon addition of Dose-Determination Phase Segment 2:
 - Changed the name for the “Dose-Escalation Phase” to “Dose-Determination Phase” to better capture the intent for this part of the study.
 - Renamed the first portion of the Dose-Determination Phase (the open-label portion) as “Segment 1” now that there are 2 segments in the Dose-Determination Phase.
 - Changed the name for the Expansion Phase cohorts to avoid confusion with Arms A and B in Dose-Determination Phase Segment 2:
 - Renamed “Cohort A” as the Abiraterone (Abi)-Resistant Cohort.
 - Renamed “Cohort B” as the Androgen-Receptor (AR)-Resistant Cohort.
- Updated eligibility criteria to allow patients with metastatic castration-resistant prostate cancer (mCRPC) with rising prostate-specific antigen (PSA).
- Added the 40-mg softgel capsule formulation of CORT125281 and the placebo capsule.
- Revised the text related to the interim safety analyses to reflect that the Data Review Committee (DRC) will evaluate data from Dose-Determination Phase Segment 2 after all patients have completed 3 cycles of treatment in this part of the study.

Table 23 Summary of Changes in Protocol CORT125281-601 Amendment 5

Section	Revision
Global changes made but not shown in the redline version	Updated the table of contents and the lists of tables and figures. Updated all of the table, figure, and section numbers. Incorporated editorial and stylistic changes as appropriate (e.g., corrected typos, added hyphens, defined acronyms). Rearranged footnotes to be in alphabetical order.
Global changes made and shown in the redline version	For the version of the protocol, changed “Amendment 4” to “Amendment 5” and changed the date from 25 July 2018 to 21 February 2020. Updated the signature page for this version. Added references to Dose-Determination Phase Segment 2 throughout the document, to reflect this added study segment. Revised End-of-Study/Early Termination (EOS/ET) to End-of-Treatment (EOT) for clarity. Revised text to clarify that “study drug” refers to CORT125281 and that “study treatment” refers to the combination of CORT125281 and enzalutamide. Removed references to including patient initials in documents (will identify patients by their unique patient identification number, not initials).
Cover Page	Removed the IND number as this is unnecessary for the protocol. Updated the Good Clinical Practice Statement.
Synopsis	Updated text in synopsis to align with changes noted in the following sections of the body of the protocol.
1.2 Therapeutic Hypothesis	Updated the citation for Kach et al. 2017 as this manuscript has been published.
1.3 CORT125281: A Glucocorticoid Receptor Antagonist	Added the international proprietary name (exicorilant).
1.3.1.1 Pharmacology Related to Mode of Action	Added the citation for Korlym prescribing information.
1.3.1.1.2 Cancer Model	Updated Figure 1 to align with the current CORT125281 IB.
1.3.2 Clinical Data	Updated text to reflect that this text reflected the knowledge at the time the study was initiated.
1.3.2.1 Clinical Update	Added this section to provide updated clinical data from recently completed CORT125281 Phase 1 studies.
1.5.1 Design Considerations	Updated this text to align with the current study design.
1.5.2 Rationale for Dose and Dose Regimen Selection	Added rationale for the evaluation of a the alternative CORT125281 dosing strategy (QD, with upward titration from a starting dose of 240 mg to 320 mg as tolerated in Arm A) in Dose-Determination Phase Segment 2.
1.5.3 Rationale for Patient Selection	Revised text to generalize and better reflect the patient population: This population is consistent with the indication for enzalutamide. Patients who have previously received enzalutamide will be allowed to participate in the Expansion Phase , as GR antagonism is intended to target one of the mechanisms of resistance to enzalutamide therapy.
1.6 Benefits and Risks	Revised text to reflect the current knowledge about benefits and risks for CORT125281 and enzalutamide.
2.3 Exploratory Objectives	Revised the exploratory objectives:

Section	Revision
	
 Evaluate the effects of CORT125281 in combination with enzalutamide on the hypothalamic pituitary-adrenal (HPA) axis, including assessments of: 
 Urinary free cortisol (UFC) Serum cortisol Plasma adrenocorticotrophic hormone (ACTH) Explore the antitumor activity of the combination of CORT125281 and enzalutamide by line of therapy and in specific sub-sets of disease, including: 
 GR positive versus GR negative, by tumor immunohistochemistry [IHC] and/or circulating tumor cells [CTCs] Androgen-receptor splice variant 7 messenger RNA (ARV7) status Systemic antagonism of cortisol activity as assessed by whole blood transcriptional profiling Assess change in PSA Conduct correlative analyses of exposure-response for measures of efficacy and changes in FK506-binding protein 5 (FKBP5) or other GC-modulated pathways, ACTH/cortisol, or other PD markers Assess the effect of the pharmacogenomics polymorphisms of the cytochrome P450 pathway on PK and PD parameters (Dose-Determination Phase Segment 1 only) Explore the effects of CORT125281 and enzalutamide on patient-reported outcomes (PRO) and quality of life (QoL)
3.1 Overall Design	
Revised this section to reflect the addition of the double-blind portion of the Dose-Determination Phase (ie, Segment 2) and to clarify that the open-label portion is now Segment 1 and the Expansion Phase is made up of the Abi-Resistant and ARant-Resistant Cohorts (renamed from Cohorts A and B).
 
Added an updated study design schematic as Figure 2.

3.1.1.1 Dose-Determination Phase Segment 1 (Open-Label)	
Added this subsection to organize text in Section 3.1.1.
 
Replaced “dose level” with “cohort”, where appropriate for clarity.

3.1.1.2 Dose-Determination Phase Segment 2 (Double-Blind)	
Added this subsection to describe the methodology for Dose-Determination Phase Segment 2.

3.1.2 Expansion Phase (Phase 2a)	
Revised text to reflect that patients in the Expansion Phase will receive CORT125281 + enzalutamide according to the RD regimen.
 
Renamed Cohorts A and B “Abi-Resistant Cohort” and “ARant-Resistant Cohort”
 
Revised the requirement for the Food-Effect Subcohort (ie, 10 patients, not necessarily the first 10 patients).
 
Added text to clarify that patients who are not in the Food-Effect Subcohort will not have a Lead-In Period.

3.2.1 Number of Patients	
Revised this text to reflect the additional patients to be enrolled for evaluation in Dose-Determination Phase Segment 2.

3.3.3 Study Duration	
Revised text to clarify that patients will receive combination treatment (CORT125281 + enzalutamide) until they reach a protocol-defined event of disease progression, experience unmanageable toxicity, or until other treatment discontinuation criteria are met.

Section	Revision
4 Study Population	Updated to reflect that patients with mCRPC with rising PSA will be allowed to enroll.
4.1 Inclusion Criteria	
Moved the Inclusion Criterion (previously #8, now Inclusion Criterion #4) for progressive disease based on PSA or imaging in Dose-Determination Phase Segment 1 and Expansion Phase.
 
Added the inclusion criterion #5 for Dose-Determination Phase Segment 2:
 
5. Dose-Determination Phase Segment 2: Currently receiving enzalutamide with a rising PSA as follows:
 
a. Rising PSA: 25% increase over nadir and an absolute value of >1 ng/mL by at least 2 measurements obtained ≥1 week apart. PSA measurements can be collected during or after the most recent prior therapy.
 
b. Patients must have received enzalutamide for a minimum of 12 weeks and be on stable doses of enzalutamide ≥80 mg QD for at least 4 weeks prior to Cycle 1 Day 1.
 
 • Patients will continue enzalutamide without interruption during the Screening Period (no wash-out period). • This will be the enzalutamide starting dose for combination with CORT125281 beginning on Cycle 1 Day 1. 
c. M0 disease is allowed.
 
Added requirement for 10 patients to have paired biopsies in Dose-Determination Segment 2 to Inclusion Criterion #10.
 
Updated Inclusion Criterion #11 to clarify the pharmacogenomic sample is only required for patients in the Dose-Determination Phase Segment 1.
 
Updated Inclusion Criterion #13 to reflect that Modification of Diet in Renal Disease (MDRD) will be used to determine creatinine clearance.

4.4 Early Patient Discontinuation of Treatment or Study Completion/Withdrawal	Revised heading to better reflect study design, in which patients are treated until reaching a protocol-defined event of disease progression or meeting other treatment discontinuation criteria but should continue in the study for Long-Term Follow-Up assessments.
4.4.1 Early Patient Discontinuation of Study Treatment	
Revised heading to better reflect study design, in which patients are treated until reaching a protocol-defined event of disease progression or meeting other treatment discontinuation criteria.
 
Added text to clarify that if a patient discontinues CORT125281 they can continue enzalutamide alone. However, if a patient discontinues enzalutamide, CORT125281 will also be discontinued.

4.4.2 Early Patient Withdrawal from Study/Study Completion	Revised heading to better reflect study design, in which patients who discontinue treatment should continue in the study for Long-Term Follow-Up assessments.
4.5 Restrictions During the Study	Revised text for clarity, and rearranged text in the last paragraph regarding contraception, to align with the order provided in the inclusion criteria.
5 Study Treatments and Management	Revised text to clarify that the co-administered drug is defined as enzalutamide, and the study treatment is CORT125281 and/or enzalutamide, as administered according to the protocol.
5.1 Study Drug (CORT125281) and Placebo	Updated text and Table 1 to reflect the addition of the 40-mg softgel capsule formulation of CORT125281 and the placebo capsule.
5.2 Non-Investigational Medicinal Agent (Enzalutamide)	Updated Table 2 to provide the dose levels for each part of the study.

Section	Revision
5.3 Timing of Study Treatment Administration	Updated text and added subheadings to clarify the timing of study treatment administration in each part of the study (Dose-Determination Phase Segments 1 and 2, and Expansion Phase). Added text to describe the recommended timing for dosing in Dose-Determination Phase Segment 2.
5.4.1 Dose-Determination Phase Segment 1 (Open-Label)	Added section heading and revised text for clarity regarding the evaluation of DLTs in Dose-Determination Phase Segment 1.
5.4.2 Dose-Determination Phase Segment 2 (Double-Blind)	Added section heading and text to describe the DLT-evaluation and dose-determination process in Dose-Determination Phase Segment 2.
5.5. Definition of Dose-Limiting Toxicities	Added text to clarify the DLT-evaluation period: DLTs will be recorded during the DLT-evaluation period (first dose of CORT125281 through completion of Cycle 1 for Segment 1, and first dose of CORT125281 through completion of Cycle 3 for Segment 2).
5.6 Maximum Tolerated Dose	Revised text to clarify that the highest dose with a DLT rate of <33% during the DLT-evaluation period will be considered the MTD.
5.7.1 CORT125281 Dose Modification or Delay	Added text to provide recommendations for dose reduction in Dose-Determination Phase Segment 2.
5.7.1.1. Continuation of Enzalutamide After CORT125281 Interruption/Discontinuation	Added this subsection to provide guidance for patients who discontinue CORT125281 but continue on enzalutamide alone.
5.8.1 Intra-Patient Dose Escalation of CORT125281	Added subsection headings to organize text clearly for Dose-Determination Phase Segments 1 and 2. Removed restriction saying CORT125281 and enzalutamide could not be simultaneously escalated.
5.8.1.2 Dose-Determination Phase Segment 2	Added this section to provide guidance on intra-patient dose escalation in Dose-Determination Phase Segment 2.
5.8.2 Intra-Patient Dose Escalation of Enzalutamide	Removed this section, as it is no longer relevant.
5.9.1 Permitted Concomitant Therapy Requiring Caution	Revised this text to clearly indicate restrictions for concomitant medications as they relate to each study treatment (CORT125281 and/or enzalutamide).
5.9.2 Prohibited Medications/Treatments/Foods	Added a link to Section 4.2 for wash-out periods for specific medications. Removed cranberry as a restricted food.
5.10 Meals and Dietary Requirements	Added Section 5.10.1 Dose-Determination Phase Segment 2 to reflect that patients should take CORT125281 with their evening meal. Added a subsection heading for the Expansion Phase to clearly organize text.
5.11 Method of Treatment Assignment and Randomization	Added subsection headings to better organize this text and added text for randomization process in Dose-Determination Phase Segment 2.
5.12 Blinding	Added subsection headings to better organize this text as it relates to each part of the study.
5.12.2.1 Unblinding	Added this section and text to cover the unblinding procedures for Dose-Determination Phase Segment 2.
5.14 Product Accountability and Treatment Adherence	Revised text to reflect that accountability will be performed on Day 1 of each cycle and at the EOT Visit.

Section	Revision
6.3.6.1 Laboratory Parameters	Revised text to clarify that the Central Laboratory Manual should be consulted for laboratory procedures. Added serum amylase, serum lipase, spot urine and UFC (both with creatinine) to the list of measurements. Moved thyroid function tests to their own column in the table, for better organization. Moved PSA to “Other” column to align with the organization in the SoA. Revised footnotes in Table 11 for clarity.
6.4 Pharmacodynamic Measures	Revised to align with the current exploratory objectives and endpoints.
6.4.1 Blood Hormones for HPA Axis Effects – 6.4.3 Circulating Tumor Cells	Revised to provide rationale for evaluating the PD endpoints in this study.
6.4.4 Paired Tumor Tissue Biopsies	Revised to reflect the need for 10 patients to have paired biopsies in Dose-Determination Segment 2.
6.4.5 Urinary Free Cortisol and Urine Spot Test	Added this subsection to describe the methods for collecting 24-hour UFC and spot urine tests.
6.6 Pharmacokinetic Measures	Added text for Dose-Determination Phase Segment 2.
6.9 Patient-Reported Outcomes and Quality-of-Life Assessments	Revised heading and text to reflect that both PRO and QoL are being evaluated in this study.
7 Study Assessments and Procedures by Study Visit	Revised to align with the current Schedules of Assessments (Appendix A)
8.1.4 Relationship to Study Treatment	Revised heading and text in this section to clearly reflect that relationship to both CORT125281 and enzalutamide will be assessed.
8.1.5 Expectedness	Revised text to describe how AE expectedness will be determined.
9.1 General Statistical Considerations	Revised this section to provide methods for analyses for Dose-Determination Phase Segment 2.
9.2 Analysis Populations and Subgroups	Correct definition of Safety Population, as this population will be used for all analyses other than evaluation of DLTs. Revised definition for DLT-Evaluable Population to reflect the addition of Dose-Determination Phase Segment 2.
9.4 Sample Size Calculation	Added subsection headings to clearly organize content for each part of the study. Added text to reflect the sample size in Dose-Determination Segment 2. Added text to reflect the replacement of patients who are not evaluable for DLTs. Revised text for the Expansion Phase to reflect the statistical calculations for the sample size of the Abi-Reistant and ARant-Resistant Cohorts.
9.5.4 Analysis of DLTs	Added text to regarding the analysis of the DLT rate (in patient-weeks).
9.6 Exploratory Analyses	Added text to reflect that additional analysis methods for PRO and QoL assessments will be outlined in the Statistical Analysis Plan.
9.8 Interim Safety Analyses Data Review Committee – 9.9 Data Review Committee Interim Safety Analyses	Reordered section headings for the Data Review Committee and Interim Safety Analyses and rearranged text to improve clarity regarding the role of the DRC in evaluating data from Dose-Determination Phase Segment 1, Dose-Determination Phase Segment 2, and the Expansion Phase.

Section	Revision
11.4 Long-Term Retention of Biological Samples	Revised text to align with current regulatory guidance on retention of patient samples.
12 References	Updated references to reflect added and updated citations in text.
Appendix A	Revised the Schedules of Assessments in Appendix A to reflect the updated study design and endpoints.
Appendix C	Removed cranberry from the list of prohibited foods. Removed text referring to the morning dose of ranitidine, as it will be restricted any time of day if it is within 1 hour of taking CORT125281.
